2.0 TRIAL DESIGN

2.1 Trial Design

This is a single center, open label trial of pembrolizumab in patients failing to respond to or relapsing after anti-CD19 chimeric antigen receptor modified T cell therapy (CTL019/CTL119) for relapsed or refractory CD19+ lymphomas.

Eligible patients will have CD19+ diffuse large B-cell, follicular, or mantle cell lymphomas with no available curative treatment options, a limited prognosis of several months to <2 years anticipated survival with currently available therapies, and progressive or relapsed disease after a single intravenous dose of $5 \times 10^8 \pm 20\%$ CTL019/CTL119 administered on our currently enrolling clinical trial (NCT02030834). We anticipate enrollment of 12 total patients onto the present trial for patients not responding to, or relapsing after, CTL019/CTL119.

[figure not shown]
The safety and efficacy of pembrolizumab in this group of patients will be determined using a fixed dose of 200mg IV. This dose was previously well-tolerated and effective for treatment of patients with metastatic melanoma and NSCLC. The primary safety endpoint will be determined by assessing the rate of pembrolizumab discontinuation as well as the rate of occurrence of treatment-related adverse events (AEs), defined as NCI CTCAE version 5 grade ≥ 3 AEs are possibly, probably, or definitely related to study treatment or grade 4 cytokine release syndrome. Secondary efficacy endpoints will be assessed, including overall response rate (ORR) and progression-free survival (PFS).

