5.2.1.2 Dose Modification

Adverse events (both non-serious and serious) associated with pembrolizumab exposure may represent an immunologic etiology. These adverse events may occur shortly after the first dose or several months after the last dose of treatment. Pembrolizumab must be withheld for drug-related toxicities and severe or life-threatening AEs as per Table 3 below. See Section 5.4 and Events of Clinical Interest Guidance Document for supportive care guidelines, including use of corticosteroids.

This document is confidential and the property of the University of Pennsylvania. No part of it may be transmitted, reproduced, published, or used by other persons without prior written authorization from the regulatory sponsor.

Table 3 Dose modification and toxicity management guidelines for immune-related AEs associated with pembrolizumab

General instructions:				

 1. Corticosteroid taper should be initiated upon AE improving to Grade 1 or less and continue to taper over at least 4 weeks. 2. For situations where pembrolizumab has been withheld, pembrolizumab can be resumed after AE has been reduced to Grade 1 or 0 and corticosteroid has been tapered. Pembrolizumab should be permanently discontinued if AE does not resolve within 12 weeks of last dose or corticosteroids cannot be reduced to ≤ 10 mg prednisone or equivalent per day within 12 weeks. 3. For severe and life-threatening irAEs, IV corticosteroid should be initiated first, followed by oral steroid. Other immunosuppressive treatment should be initiated if irAEs cannot be controlled by corticosteroids. 				
Immune-related AEs	Toxicity grade or conditions (CTCAEv5.0)	Action taken to pembrolizumab	irAE management with corticosteroid and/or other therapies	Monitor and follow-up
Pneumonitis	Grade 2	Withhold	
 • Administer corticosteroids (initial dose of 1-2 mg/kg prednisone or equivalent) followed by taper 	
 • Monitor participants for signs and symptoms of pneumonitis • Evaluate participants with suspected pneumonitis with radiographic imaging and initiate corticosteroid treatment • Add prophylactic antibiotics for opportunistic infections
	Grade 3 or 4, or recurrent Grade 2	Permanently discontinue		

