At this time it is still unknown whether CRS/MAS is beneficial or harmful to the antitumor response. Research monitoring data showed that IL6 levels were extraordinarily high during the CRS, prompting us to use an anti-IL6 receptor antibody tocilizumab to treat the CRS/MAS. The majority of patients treated with tocilizumab for CRS and MAS had rapid (within hours) resolution of dramatic fevers, and continuous improvement in hypotension and hypoxia over hours to several days, and showed improvement in biochemical evidence of CRS and MAS within 48 hours. Adult patients were treated with tocilizumab 4mg/kg or 8mg/kg. It is unclear if early treatment will negate the antitumor response. Treatment and timing of treatment of this toxicity will be at the discretion of the patient's physician and the study principal investigator, and occur in the setting of hemodynamic instability.

Management of cytokine release syndrome

Some patients who have responded to CART-19 cells have experienced a CRS. Cytokine production is required for the activation, expansion and cytolytic function of T cells and for CART-19 T cells. Therefore some degree of CRS may be a desired clinical outcome. Premature or early intervention with anti-cytokine therapy may therefore abrogate the anti-tumor efficacy of CART-19. Subsequent to this experience, selective tocilizumab (an anti-IL6-receptor antibody) therapy has been utilized (described below) with effective toxicity management and successful ongoing CART-19 T cell expansion in patients. Please note, steroids or other immunosuppressant drugs should **NOT** be used as pre-medication for pembrolizumab but may be considered in the management of CRS.

The moderate to severe cases of CRS observed required intervention with tocilizumab, with or without high dose corticosteroids, between 2 and 9 days after T cell infusion. This resulted in rapid reversal of the high persistent fevers associated with CRS in most but not all patients.

Given the dramatic clinical improvement of most patients treated with anti-cytokine therapy, patients with moderate to severe cytokine toxicities should be first managed with administration of tocilizumab.

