7.3.2 Evaluating Adverse Events

An investigator who is a qualified physician will evaluate all adverse events according to the NCI Common Terminology for Adverse Events (CTCAE), version 5.0. Any adverse event which changes CTCAE grade over the course of a given episode will have each change of grade recorded on the adverse event case report forms/worksheets.

If CTCAE grading does not exist for an adverse event, the severity of mild, moderate, severe, and life-threatening, corresponding to Grades 1-4, will be used. Subjects will be monitored by medical histories, physical examinations, and blood studies to detect potential toxicities from the treatment.

Table 6 Evaluating Adverse Events

An investigator who is a qualified physician, will evaluate all adverse events as to:

V5.0 CTCAE Grading	Grade 1	Mild; asymptomatic or mild symptoms; clinical or diagnostic observations only; intervention not indicated.
	Grade 2	Moderate; minimal, local or noninvasive intervention indicated; limiting age-appropriate instrumental ADL.
	Grade 3	Severe or medically significant but not immediately life-threatening; hospitalization or prolongation of hospitalization indicated; limiting self-care ADL.
	Grade 4	Life threatening consequences; urgent intervention indicated.
	Grade 5	Death related to AE
Seriousness	A serious adverse event is any adverse event occurring at any dose or during any use of pembrolizumab that:	
	† Results in death ; or	
	† Is life threatening ; or places the subject, in the view of the investigator, at immediate risk of death from the event as it occurred (Note: This does not include an adverse event that, had it occurred in a more severe form, might have caused death.); or	
	† Results in a persistent or significant disability/incapacity (substantial disruption of one's ability to conduct normal life functions); or	
	† Results in or prolongs an existing inpatient hospitalization (hospitalization is defined as an inpatient admission, regardless of length of stay, even if the hospitalization is a precautionary measure for continued observation. (Note: Hospitalization [including hospitalization for an elective procedure] for a preexisting condition which has not worsened does not constitute a serious adverse event.); or	
	† Is a congenital anomaly/birth defect (in offspring of subject taking the product regardless of time to diagnosis); or	

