8.0 STATISTICAL ANALYSIS PLAN

8.1 Statistical Analysis Plan

8.1.1 Primary Objectives & Hypotheses

(1) Objective: To determine the safety of pembrolizumab in patients failing to respond to or relapsing after anti-CD19 chimeric antigen receptor modified T cell therapy for relapsed or refractory CD19+ lymphomas. Safety will be assessed by adverse event monitoring. Patients who have received at least one dose of pembrolizumab will be considered evaluable for safety. In this trial, success will be defined as receiving at least one dose of pembrolizumab and the lack at least possibly related adverse events leading to permanent discontinuation of pembrolizumab. Patients who experience Grade 3 or higher non-hematologic toxicity leading to permanent pembrolizumab discontinuation or any Grade 4 non-hematologic toxicity or cytokine release syndrome at least possibly related to pembrolizumab will be considered toxicity failures.

Methodology: We will use a Bayesian monitoring rule to assure that the failure rate is no greater than 30%. Monitoring will begin with the first patient. Because little information is available on the safety of this drug in lymphoma, we will assume a non-informative Beta(1, 1) prior distribution for the failure rate. We will denote the rate of pembrolizumab discontinuation as failure rate, FR, and will use the following monitoring rule in the interest of patient safety: we will stop the trial if at any time: $\Pr[\text{FR} > 0.30 \mid \text{data from the trial}] \geq 97.5\%$

That is, if at any time during the study, we can conclude that there is at least a 97.5% chance that the failure rate is greater than 30%, we will stop the study. The stopping boundaries corresponding to this probability criterion are to terminate the trial if:

$(\# \text{ of patients that experience failure}) / (\# \text{ of patients evaluated}) \geq 3/3, 3/4, 4/5, 4/6, 5/7, 5/8, 6/9, 6/10, 7/11, 7/12$. Any patient who has received at least one dose of pembrolizumab will be included in this denominator for evaluable patients if they have received at least 4 doses of pembrolizumab and not experienced toxicity OR if they have experienced any toxicity with any dose of pembrolizumab.

If the study is not terminated early, it will continue until all patients have been treated with pembrolizumab and completed all follow up evaluations.

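### The limb of the toxicity-failure rule that needs no discontinuation names Grade 4 only, so a related off-drug death with no recorded Grade 4 stage is not a failure; its CRS wording also has two readings

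*Combined protocol and SAP*

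**What the plan says.** Section 8.1.1 defines toxicity failures in one sentence with two limbs. It opens "Patients who experience Grade 3 or higher non-hematologic toxicity leading to permanent pembrolizumab discontinuation or any Grade 4 non-hematologic toxicity or cytokine release syndrome", and its second limb reads in full "any Grade 4 non-hematologic toxicity or cytokine release syndrome at least possibly related to pembrolizumab will be considered toxicity failures". Limb 1 is open at the top (Grade 3 or higher) but requires permanent discontinuation. Limb 2 requires no discontinuation but names Grade 4 alone.

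The same section defines success as at least one dose and "the lack at least possibly related adverse events leading to permanent discontinuation of pembrolizumab". It then describes the monitored quantity FR as the discontinuation rate.

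Other sections bear on the rule:

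- **Grade 5 is a separate grade.** Table 6 in section 7.3.2 gives it as "Death related to AE", and the CRS scale in Table 7.2.5a (section 7.3.3) also has a separate column for death.
- **Late events are expected.** Section 5.2.1.2 says of pembrolizumab-associated events: "These adverse events may occur shortly after the first dose or several months after the last dose of treatment". Section 5.6 collects serious events for 90 days after treatment ends.
- **Section 2.1 words the safety endpoint differently.** It takes the discontinuation rate together with AEs of grade 3 or above that are "possibly, probably, or definitely related to study treatment or grade 4 cytokine release syndrome".
- **Section 5.4.2 on CRS** says: "Therefore some degree of CRS may be a desired clinical outcome".

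**The concern.** The failure count decides whether the primary safety endpoint (no more than 30%) is met, and it drives the Bayesian stopping rule. A rule of this kind should not leave out the worst grade.

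Limb 1 cannot apply once pembrolizumab has been stopped for progression, complete response or completion, because the event did not cause the stop. Only limb 2 remains, and it ends at Grade 4. A related death in that period then meets neither limb and fits the literal definition of success. The patient stays in the denominator, which includes anyone with any toxicity at any dose, and so enters as an evaluated non-failure.

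The same clause is also unclear about CRS, which the protocol names as a specific risk of this treatment sequence. Two people applying it to the same records could report different failure counts.

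**Working it through.** **1. The plan's own figures.** The inputs from section 8.1.1 are a Beta(1,1) prior, stopping when Pr[FR > 0.30 | data] ≥ 0.975, and the listed boundaries. With x failures in n patients, FR follows Beta(1+x, 1+n−x), so Pr[FR > 0.30] = P(Bin(n+1, 0.30) ≤ x).

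| Boundary | Posterior | One failure fewer |
|---|---|---|
| 3/3 | 0.992 | 0.916 |
| 3/4 | 0.969 | 0.837 |
| 4/5 | 0.989 | 0.930 |
| 4/6 | 0.971 | 0.874 |
| 5/7 | 0.989 | 0.942 |
| 5/8 | 0.9747 | 0.901 |
| 6/9 | 0.989 | 0.953 |
| 6/10 | 0.978 | 0.922 |
| 7/11 | 0.991 | 0.961 |
| 7/12 | 0.982 | 0.938 |

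Seven of the ten meet 0.975. The boundaries 3/4 and 4/6 fall short, and 5/8 reaches it only after rounding. These three stop earlier than the stated criterion requires. That is a separate matter and does not affect this point.

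**2. The rule applied to records.** In each record pembrolizumab was stopped for progression, and a related non-hematologic event follows within 90 days.

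| Record | Limb 1 | Limb 2 | Literal result | Related grade ≥ 3 (2.1) |
|---|---|---|---|---|
| Reaches Grade 4, survives | no | yes | failure | counted |
| Grade 4 recorded, then Grade 5 | no | yes | failure | counted |
| Recorded directly as Grade 5, or Grade 3 then 5 | no | no | not a failure | counted |

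Only the third row is a gap. The second row counts because section 7.3.2 requires each change of grade to be recorded.

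**3. The CRS wording.** The clause supports two readings.

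- *Reading A: the words Grade 4 govern both nouns.* This matches the CRS phrase in section 2.1. CRS of Grade 1 to 3 that does not end treatment is not a failure, and off-drug fatal CRS with no recorded Grade 4 stage is not counted either.
- *Reading B: the words Grade 4 govern only the non-hematologic toxicity.* CRS of any grade is a failure. Fatal CRS counts, but so does Grade 1 CRS managed with antipyretics.

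A patient with Grade 1 CRS that resolves, who then restarts the drug as section 5.2.1.2 allows, is a non-failure under A and a failure under B. The remark on CRS in section 5.4.2 fits A better, but section 8.1.1 does not settle it.

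**4. Effect of one reclassified death.** It adds 1 to x and leaves n unchanged.

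- Endpoint at n = 12: 3/12 = 25.0% (met; posterior 0.421) becomes 4/12 = 33.3% (not met; 0.654).
- Boundary at n = 12: 6/12 (0.938, continue) becomes 7/12 (0.982, stop).
- Boundary during accrual: 3/5 (0.930, continue) becomes 4/5 (0.989, stop), and 5/9 (0.953, continue) becomes 6/9 (0.989, stop).

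The documents give no rate for such deaths, so an expected effect cannot be computed.

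**The case against.** Five arguments narrow the point.

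- **Most fatal events pass through Grade 4.** Table 6 defines Grade 4 by life-threatening consequences, and every grade change is recorded. This stands. The gap is a related off-drug death with no Grade 4 entry.
- **Fatal CRS on treatment is largely caught already.** Section 5.2.1.2 ends pembrolizumab for toxicity if CRS reaches Grade 4 or tocilizumab is required, so limb 1 applies to CRS of Grade 3 or higher handled that way. The pressor and ventilation criteria for Grade 4 in Table 7.2.5a are given as examples, so a CRS that proves fatal would often have been graded 4 first. This stands.
- **Fatal CRS cannot be omitted if CRS of any grade counts.** This also stands. The two CRS defects are alternatives, one under each reading.
- **Sections 1.0, 3.1 and 4.2.3.1, and the FR wording in 8.1.1, define the endpoint by discontinuation.** On that definition neither Grade 4 nor Grade 5 off-drug events count, and the asymmetry disappears. But the explicit failure sentence in 8.1.1 does count Grade 4 without discontinuation. The plan therefore holds two definitions, and the objection shows that they need reconciling.
- **A death would not go unseen.** Unexpected deaths go to the data and safety monitoring committee within two business days (7.3), the medical monitor may recommend stopping (10.4), and section 5.9 allows termination on the severity of adverse reactions. This protects patients, but it does not put the death into the endpoint or the posterior.

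A reader might infer that the rule generally scores death as better than survival, or that CRS deaths on treatment escape it. The first and second arguments show that the documents do not support either. A reader might also want a probability that this happens. It would have to rest on invented event rates, or on treating every non-responder as off drug. Non-response does not mean that: stable patients may continue, and section 5.6 allows treatment beyond progression.

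**Conclusion.** The point holds in limited form. Followed literally, section 8.1.1 leaves out a related non-hematologic death after pembrolizumab was stopped for another reason, when no Grade 4 stage was recorded. It counts the same event survived at Grade 4, and it disagrees with section 2.1, whose related grade ≥ 3 criterion covers the death. The CRS wording is separately ambiguous and gives different counts under its two readings.

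This is most likely a drafting gap, with Grade 4 or higher intended. The event is probably rare. The case for correcting it is that one patient in 12 is 8.3 percentage points (1/12), enough to move the safety endpoint from met to not met or to cross a stopping boundary. The sizes in the working assume that the other failures fall just short of the relevant threshold. They show what one death can do, not what is expected.

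**What to change.** In section 8.1.1, replace limb 2 with: *any Grade 4 or higher non-hematologic toxicity, or Grade 4 or higher cytokine release syndrome (Table 7.2.5a), judged at least possibly drug-related, whether on treatment or within the protocol's adverse-event collection period*. Name that period by reference to section 7.2.3.1, which sets 90 days after the last dose or the start of new anti-cancer therapy, whichever is earlier.

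Make this the single failure definition. State success as its complement, define FR as the rate of these failures instead of the discontinuation rate, and align the safety-endpoint wording in section 2.1. The discontinuation wording in the trial summary and the primary hypothesis should then refer to the same definition.

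The change concerns only how outcomes are counted. No dosing or management rule changes, the stopping boundaries stay as they are, and no new data are needed because serious related events are already collected. The cost is a few short edits and a reported failure rate that may be slightly less favourable.

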10.4 Quality and Safety Management

It is the responsibility of the Principal Investigator to oversee the safety of the study at his/her site. This safety monitoring will include careful assessment and appropriate reporting of adverse events as noted above, as well as the construction and implementation of a site data and safety-monitoring plan. This will include a regular assessment of the number and type of serious adverse events.

The investigator will permit study-related monitoring, audits, and inspections by the DSMC, IRB, government regulatory bodies, and University compliance and quality assurance groups of all study related documents (e.g. source documents, regulatory documents, data collection

This document is confidential and the property of the University of Pennsylvania. No part of it may be transmitted, reproduced, published, or used by other persons without prior written authorization from the regulatory sponsor.

instruments, study data etc.). The investigator will ensure the capability for inspections of applicable study-related facilities (e.g. pharmacy, diagnostic laboratory, etc.).

Interim analyses of toxicity are to be performed quarterly or every three patients on-study. The Abramson Cancer Center Data and Safety Monitoring Committee will conduct in-house safety audits as per their guidelines.

During the course of the trial, safety and data quality monitoring will be performed in an ongoing manner by the Principal Investigator. The principal investigator will monitor data integrity. This includes ensuring that all source documents exist for the data on the case report forms, ensuring that all fields are completed appropriately, all corrections are done according to GCPs and any inconsistencies / deviations are documented. The Principal Investigator will also review all Adverse Event forms in “real-time” to ensure appropriateness of the data and timeliness of reporting.

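### Three of the ten printed safety stopping boundaries (3/4, 4/6 and, by a rounding-level margin, 5/8) do not meet the 97.5% Bayesian criterion they are said to represent

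*Combined protocol and SAP*

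**What the plan says.** Section 8.1.1 of the combined protocol and SAP (Methodology under the primary objective) sets out the safety monitoring rule in three parts.

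- Prior: "we will assume a non-informative Beta(1, 1) prior distribution for the failure rate".
- Criterion: if at any time "there is at least a 97.5% chance that the failure rate is greater than 30%, we will stop the study".
- Boundaries: "The stopping boundaries corresponding to this probability criterion are to terminate the trial if" failures over patients evaluated reach "3/3, 3/4, 4/5, 4/6, 5/7, 5/8, 6/9, 6/10, 7/11, 7/12".

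The same section says "Monitoring will begin with the first patient". Section 10.4 adds a periodic review: "Interim analyses of toxicity are to be performed quarterly or every three patients on-study". The Trial Summary (Section 1.0) gives the sample size as 12 evaluable subjects. The plan states no rounding convention, no second cutoff and no minimum number of patients before stopping is possible.

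**The concern.** The printed counts are presented as a translation of the probability criterion, so each should be the smallest number of failures at which the posterior reaches 97.5%. If some are not, the plan contains two different stopping rules for its primary safety endpoint. Both are worded as binding, and nothing says which takes precedence. Should the failures land on a count where they differ, the choice would be made after the toxicity data were known, in an open-label single-arm trial. The plan's true chance of stopping early would also be unclear, and an early stop cuts the 12 patients on which the response-rate test in Section 8.1.2 depends.

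**Working it through.** **Inputs**, all from Sections 8.1.1 and 1.0: prior Beta(1,1); threshold 0.30; cutoff 0.975; monitoring from patient 1 at any time; maximum n = 12.

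**Formula.** With s failures in n patients the posterior is Beta(1+s, 1+n−s). For whole-number counts, Pr(FR > 0.30 | s, n) = P(Bin(n+1, 0.30) ≤ s) = 1 − P(Bin(n+1, 0.30) ≥ s+1).

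**The three counts that fail:**

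- 3/4: 1 − [5(0.3⁴)(0.7) + 0.3⁵] = 1 − (0.02835 + 0.00243) = 0.96922
- 4/6: 1 − [21(0.3⁵)(0.7²) + 7(0.3⁶)(0.7) + 0.3⁷] = 1 − (0.0250047 + 0.0035721 + 0.0002187) = 0.97120
- 5/8: 1 − [84(0.3⁶)(0.7³) + 36(0.3⁷)(0.7²) + 9(0.3⁸)(0.7) + 0.3⁹] = 1 − 0.025295 = 0.97471

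**The full list:**

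| Printed boundary | Posterior | Posterior with one failure fewer | Meets 0.975? | Smallest count meeting 0.975 |
|---|---|---|---|---|
| 3/3 | 0.9919 | 0.9163 | yes | 3/3 |
| 3/4 | 0.9692 | 0.8369 | no | 4/4 |
| 4/5 | 0.9891 | 0.9295 | yes | 4/5 |
| 4/6 | 0.9712 | 0.8740 | no | 5/6 |
| 5/7 | 0.9887 | 0.9420 | yes | 5/7 |
| 5/8 | 0.9747 | 0.9012 | no (by 0.0003) | 6/8 |
| 6/9 | 0.9894 | 0.9527 | yes | 6/9 |
| 6/10 | 0.9784 | 0.9218 | yes | 6/10 |
| 7/11 | 0.9905 | 0.9614 | yes | 7/11 |
| 7/12 | 0.9818 | 0.9376 | yes | 7/12 |

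Seven of the ten are reproduced as correct minimum counts.

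**Could another setting have produced the list?** Under Beta(1,1), including 3/4 needs a cutoff of at most 0.9692, and excluding 6/11 needs one above 0.9614. Any cutoff in that range gives the printed counts for n = 3 to 12. It also stops at 2/2, where the posterior is 1 − 0.3³ = 0.9730, and 2/2 is not printed. So no single Beta(1,1) cutoff applied from the first patient gives this list. Other priors tried at 0.975, including Beta(0.5, 0.5), did not reproduce it either.

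**Effect on stopping.** Exact calculation over 12 sequential patients, with the boundary checked after each one:

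| True FR | P(stop), list | P(stop), 97.5% criterion | Difference |
|---|---|---|---|
| 10% | 0.4% | 0.1% | 0.3 points |
| 20% | 3.8% | 1.8% | 2.0 points |
| 30% | 13.4% | 8.5% | 4.9 points |
| 40% | 31.3% | 24.2% | 7.1 points |
| 50% | 55.0% | 48.2% | 6.8 points |

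Enumerating all 4096 outcome sequences, the list never stops later than the criterion. The difference column is therefore the share of trials whose final stop-or-complete outcome changes.

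**How often would the trial reach a disputed count?** At FR 30%:

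- 3/4 without a prior 3/3: 3(0.3³)(0.7) = 0.0567
- 4/6 (two failures in the first four, then two more): 6(0.3²)(0.7²)(0.3²) = 0.0238
- 5/8: 16 paths × (0.3⁵)(0.7³) = 0.0133

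The total is 0.0938, or 9.4%. The corresponding figures are 2.8% at FR 20%, 20.6% at 40% and 34.4% at 50%.

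**Patients evaluated, list against criterion.** The mean is 11.1 against 11.5 at FR 30%, and 8.5 against 9.5 at FR 50%. The chance of reaching the 12th patient at FR 50% is 48.5% against 56.8%.

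**The case against.** Five points can be made for the plan.

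1. **The list errs towards caution.** This stands. Following it exposes no patient to more risk than the 97.5% criterion allows. It limits the harm but does not make the two rules agree.
2. **The list reads as the operating instruction, so a committee at 3/4 would stop.** That is a reasonable reading. But the criterion is also written as a commitment to stop at a stated probability, and the list claims only to express it. Precedence is not stated.
3. **5/8 passes if the posterior is rounded to one decimal of a percent.** True. Accepting it leaves two clear mismatches, 3/4 (96.9%) and 4/6 (97.1%), and moves the criterion's chance of stopping at FR 30% from 8.5% to 9.5%.
4. **The disagreement probabilities look larger than their consequence.** Partly right. At FR 50%, 34.4% of trials reach a disputed count, but only 6.8% end differently. In the remaining 34.4 − 6.8 = 27.6 points both versions stop, at different times.
5. **The size depends on when the boundary is checked.** Also right. If it were applied only at n = 3, 6, 9 and 12, one reading of Section 10.4, only 4/6 would matter, and the chance of stopping at FR 30% would be 9.8% against 6.5%. Section 8.1.1 applies the rule at any time, which supports checking after each patient.

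The absence of 2/2 is not an error under the stated criterion, since 0.9730 is below 0.975. It matters only if the list is kept and the cutoff lowered to fit it.

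**Conclusion.** The concern holds. Two printed boundaries (3/4 and 4/6) clearly miss the stated 97.5% criterion, and a third (5/8) misses by 0.0003. The list therefore stops earlier than the rule it claims to express, by 4.9 percentage points at a true FR of 30% and 6.8 points at 50%. The posterior values follow from Section 8.1.1 alone and need no outside assumption. The stopping probabilities assume independent patients with a common failure rate, 12 evaluable patients, and a check after each becomes evaluable. Because the inconsistency sits in the stopping rule for the primary safety endpoint, it should be settled before the rule has to be applied.

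**What to change.** State in Section 8.1.1 whether the list or the probability criterion governs, and make them agree. The choice is the sponsor's.

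- **Option 1: keep 97.5%.** Print 3/3, 4/4, 4/5, 5/6, 5/7, 6/8, 6/9, 6/10, 7/11, 7/12. With a check after every patient, 4/4, 5/6 and 6/8 can be reached only through 3/3, 4/5 and 5/7 or worse, which already stop the trial, so no new stop can occur at n = 4, 6 or 8. The chance of stopping at FR 30% is 8.5% instead of the list's 13.4%.
- **Option 2: keep the printed list.** Restate the cutoff as about 96.9% (above 0.9614, at most 0.9692) and deal with 2/2.
  - If 2/2 is added, the chance of stopping becomes 6.2%, 17.2%, 35.3% and 58.1% at FR 20%, 30%, 40% and 50%.
  - If stopping is first assessed at n = 3, the list's probabilities above are unchanged, but the sentence on monitoring from the first patient needs to say so.

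Report the stopping probabilities for the chosen version. Add a cross-reference to Section 10.4 making clear that the boundary is checked whenever a patient becomes evaluable, not only at periodic reviews. The cost is a wording change and one recomputed line, with no additional patients.
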